8.3.4 Summary of the Risks and Benefits

As renal function is an important prognostic factor in patients with AHF, the patients randomized to the treatment groups may potentially benefit from the study. The risks of the study are:

- Low dose dopamine: **Common**: Chest pain, increase in blood pressure, fast or irregular heart rates, injection site reaction and hair follicles could stand erected
- Low dose nesiritide: **Common:** Low blood pressure nausea, dizziness; headache; insomnia; worsening of renal function at doses that are higher than what is used in this study. **Uncommon:** irregular heart rhythm, allergic reaction and increased risk of death
- The risks of blood drawing include bleeding at the puncture site, bruising and pain. These risks occur in a very small portion of the population. Patients with a hemoglobin < 9 g/dl will be excluded.
- The risk for PICC line placement include bruising, fainting, pain, swelling, scarring, bleeding, infection, a decrease in blood pressure, slowing of heartbeats, sweating and a feeling of weakness or lightheadedness. Uncommon risk includes infection at the site of the needle stick. These reactions generally do not cause any permanent harm. If a central line is needed, there may be additional risk of pneumothorax.
- This protocol may be hazardous to an unborn child. There is no medical information to determine whether there are significant risks to a fetus carried by a mother who is participating in this study. Therefore, female participants must be postmenopausal or have been surgically sterilized or have a serum negative pregnancy test.

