- Not Possibly Related: It is unlikely that the event was caused by the study intervention. The temporal relationship of the adverse event to the study intervention makes causal relationship unlikely and other drugs, therapeutic interventions or underlying conditions provide a more likely explanation for the event.

An Unexpected Adverse Event: is when the nature or severity of the event is not consistent with the applicable study intervention, expected clinical course or current product labeling.

The following adverse events are anticipated, disease related-events in patients with acute decompensated heart failure and therefore do not require reporting on the Adverse Event form of the CRF (although some may require reporting as study endpoints):

- Atrial fibrillation
- Ventricular tachycardia
- Myocardial infarction
- Acute coronary syndrome
- Electrolyte disturbance
- Acute renal failure
- Worsening heart failure

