12.4.2 Recording and Reporting

The Site Investigator is responsible for monitoring the safety of patients enrolled into the study at the study sites. All SAEs will be documented in the source documents and, with the exception of the anticipated events, captured on the SAE page of the CRF. Non-serious AEs should be documented in the source documents and followed according to local standard of care.

All SAEs that result in death or are unexpected for and related to study drug (dopamine or nesiritide) must be reported on a HFN Expedited Event form and faxed to DCRI Safety Surveillance at [name].

Additionally, adverse events which meet the criteria of serious, related to study drug (dopamine or nesiritide), and unexpected for that drug, qualify for expedited reporting to the regulatory authorities. The Site Investigator will assess all SAEs occurring at his/her site and evaluate for "unexpectedness" and relationship to study drug. The Site Investigator is required to complete and submit a voluntary MedWatch Report for the events identified as serious, study drug related and unexpected at https://www.accessdata.fda.gov/scripts/medwatch/. A copy of this report should be kept at the site and also forwarded to the Data Coordinating Center.

Investigators are also responsible for promptly reporting adverse events to their reviewing IRB/EC in accordance with local requirements.

A Data and Safety Monitoring Board (DSMB) will review detailed safety data at regular intervals throughout the study.

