13.6 Statistical Monitoring Plan

Interim data analysis for efficacy will not be conducted due to relatively small size and short duration of this phase II clinical trial. Safety data will be periodically assessed by the Data and Safety Monitoring Board based on reporting of adverse events and treatment-level summary data.

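### Non-fatal serious atrial fibrillation, ventricular tachycardia, myocardial infarction and acute coronary syndrome mostly have no required CRF event record, so a count by arm is not assured

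*Protocol*

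**What the plan says.** Section 12.4.1 (Definitions) names atrial fibrillation, ventricular tachycardia, myocardial infarction, acute coronary syndrome, electrolyte disturbance, acute renal failure and worsening heart failure. It calls them "anticipated, disease related-events in patients with acute decompensated heart failure and therefore do not require reporting on the Adverse Event form of the CRF", and adds that some may still be reported as endpoints.

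Section 12.4.2 (Recording and Reporting) extends the exemption to serious cases: SAEs are, "with the exception of the anticipated events, captured on the SAE page of the CRF". For all other events that are not serious it says: "Non-serious AEs should be documented in the source documents and followed according to local standard of care".

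Section 8.3.4 lists the drug risks. For dopamine the common ones begin "Chest pain, increase in blood pressure, fast or irregular heart rates". For nesiritide the uncommon ones are "irregular heart rhythm, allergic reaction and increased risk of death".

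Section 13.6 says that the DSMB will assess safety periodically, "based on reporting of adverse events and treatment-level summary data". Section 12.4.2 adds that the board will see detailed safety information at regular intervals. Neither section says what these data contain.

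**The concern.** Exempting anticipated disease events from expedited reporting is ordinary practice. Here the exemption goes further and takes the events off the CRF event pages altogether. Two of them, atrial fibrillation and ventricular tachycardia, are rhythm disturbances, and the protocol itself lists rhythm disturbance as a risk of both study drugs.

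A blinded investigator looking at one patient with atrial fibrillation cannot tell drug effect from disease. Only a comparison of counts between randomized arms can do that, and it needs the events in the database. The Executive Summary states the objective as safety as well as efficacy, yet the only primary safety measure is cystatin C. This cannot be left to a SAP, because an analysis plan cannot tabulate events that the CRF was told not to collect.

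**Working it through.** The point rests on no stated figure, so the check is to follow one type of case through every recording route in the protocol. The case is a serious, non-fatal atrial fibrillation, ventricular tachycardia, myocardial infarction or acute coronary syndrome.

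1. **AE form (12.4.1).** Closed: all four are on the exempt list.
2. **SAE page (12.4.2).** Closed: the anticipated events are excepted even when serious. This is the step that matters. Section 12.4.2 leaves every non-serious event in source documents, listed or not, so for non-serious cases the exempt list changes nothing.
3. **Endpoints (11.1 to 11.3).** None of the four is named as a primary, secondary or tertiary endpoint. The other three exempt events are covered at least in part: worsening heart failure by an endpoint, acute renal failure by the creatinine and cystatin C endpoints, and electrolyte disturbance by scheduled laboratory tests. So four of seven exempt categories have no endpoint or laboratory measure of their own.
4. **Treatment failure composite (11.2).** Partly open. It counts tachycardia that leads to stopping study drug, as well as rescue therapy for heart failure, hypotension that stops study drug, and death. A case may enter through one of these, but it is not recorded as the arrhythmia or infarction that caused it.
5. **Expedited Event form (12.4.2).** Open for deaths, with no exception for anticipated events, and for SAEs that are both unexpected and related. Under 12.4.1 an event is unexpected when its nature or its severity is out of line with the drug, the disease course or the labelling. An event already called anticipated, or listed as a drug risk, will seldom qualify, though an unusually severe one could.
6. **Schedule (Appendix A).** No ECG is listed. The event row is for serious adverse events, which is the stream from which these four are removed. Vital signs and cardiovascular medication are collected, but they are indirect.

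**Evenness of route 4.** The heart-rate stopping rule in section 7.4 is written for the Dopamine strategy group only. With 360 patients, 1:1 between strategies and 2:1 within each:

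- Each strategy: 360 / 2 = 180 patients.
- Active drug per strategy: 180 × 2/3 = 120. Placebo per strategy: 180 × 1/3 = 60.
- Covered by the rule: 120 on dopamine and 60 on placebo.
- Not covered by it: 120 on nesiritide and the other 60 on placebo.

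The rule therefore applies to the whole dopamine arm, to none of the nesiritide arm, and to 60 / 120 = half of the pooled placebo group. A comparison with pooled placebo on this component would mix two capture rules.

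**Result.** A non-fatal serious case that does not stop study drug for tachycardia, and is not judged both unexpected and related, has no CRF event record that the protocol requires.

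**The case against.** The strongest reply is that important cases do reach the database. Fatal cases go on the expedited form, and mortality is followed to six months. Tachycardia that ends the infusion counts as treatment failure in the strategy group where irregular rhythm is a common listed risk. An unusually severe related arrhythmia can be judged unexpected. All of this stands, and it limits the point to the remaining non-fatal serious cases.

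A reader might infer that the DSMB cannot see arrhythmia or ischaemia by arm at all. The protocol does not support that. Section 13.6 gives the board summary data by treatment as well as event reports, and section 12.4.2 promises detailed safety information. Neither is defined, and the CRF and any DSMB charter are not at hand. What can be said is that no section requires these four events to be among the data.

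A reader might also infer that the exempt list matches the listed drug risks. It does so only in part. Chest pain is not exempt, so serious chest pain not classed as infarction or acute coronary syndrome still goes on the SAE page, and it is listed for dopamine only. Myocardial infarction and acute coronary syndrome are not listed as risks of either drug. The real overlap is atrial fibrillation and ventricular tachycardia.

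Finally, the protocol gives a reason for the exemption: these events are anticipated in this disease. That justifies not expediting them. It does not justify leaving them uncounted in a placebo-controlled comparison.

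**Conclusion.** The point holds as a gap in required data collection. Four of the seven exempt categories have no AE form, SAE page or endpoint of their own. Non-fatal serious cases are recorded as events only if study drug is stopped for tachycardia, or if they are judged both unexpected and related. The first of these routes does not identify the rhythm and is uneven across arms. The protocol therefore does not assure the DSMB or the final report a count by arm of events that include a listed risk of both drugs.

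The protocol gives no rates for these events, so the number of unrecorded cases cannot be estimated; any count would rest on assumed rates. The conclusion assumes that the CRF follows sections 12.4.1 and 12.4.2 as written. If the CRF already has a page for these events, the protocol text should be brought into line with it.

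**What to change.** Keep the exemption from expedited reporting. Amend sections 12.4.1 and 12.4.2 so that atrial fibrillation, ventricular tachycardia, myocardial infarction and acute coronary syndrome are recorded on one CRF event page for every patient. The period would run from randomization to Day 7, or to discharge if earlier, with three fields per event: yes/no, date, and serious yes/no. State in section 13.6 that these events are tabulated by arm within strategy for the DSMB, and that the same table goes in the final report. Tabulating within strategy compares each drug first with the placebo patients managed under the same rules.

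The cost is one short CRF page, one DSMB table and a little extra data entry at sites. Serious cases must already be in source documents under section 12.4.2. Nothing in dosing, stopping rules or patient management changes.

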12.4.2 Recording and Reporting

The Site Investigator is responsible for monitoring the safety of patients enrolled into the study at the study sites. All SAEs will be documented in the source documents and, with the exception of the anticipated events, captured on the SAE page of the CRF. Non-serious AEs should be documented in the source documents and followed according to local standard of care.

All SAEs that result in death or are unexpected for and related to study drug (dopamine or nesiritide) must be reported on a HFN Expedited Event form and faxed to DCRI Safety Surveillance at [name].

Additionally, adverse events which meet the criteria of serious, related to study drug (dopamine or nesiritide), and unexpected for that drug, qualify for expedited reporting to the regulatory authorities. The Site Investigator will assess all SAEs occurring at his/her site and evaluate for "unexpectedness" and relationship to study drug. The Site Investigator is required to complete and submit a voluntary MedWatch Report for the events identified as serious, study drug related and unexpected at https://www.accessdata.fda.gov/scripts/medwatch/. A copy of this report should be kept at the site and also forwarded to the Data Coordinating Center.

Investigators are also responsible for promptly reporting adverse events to their reviewing IRB/EC in accordance with local requirements.

A Data and Safety Monitoring Board (DSMB) will review detailed safety data at regular intervals throughout the study.

13. STATISTICAL CONSIDERATIONS

13.1 Overview

Summaries of continuous variables will be displayed using the mean, standard deviation, median, and 25th - 75th percentiles. For nominal variables, the number and frequency of subjects in each category will be presented. Statistical tests with p-values < 0.05 will be considered statistically significant, unless otherwise stated. Analyses will be performed using SAS software (SAS Institute, Inc, Cary, NC).

13.2 Analysis of Primary Endpoints

The primary analysis will be conducted on an intention-to-treat basis. A general linear model with an indicator for randomization to the nesiritide strategy or dopamine strategy, as well as an indicator for the specific treatments being compared, will be used to examine the effect of each treatment on the primary safety and efficacy outcomes. For the primary comparisons, placebo subjects will be pooled across the nesiritide and dopamine strategies. Comparisons of low-dose dopamine vs. placebo and low-dose nesiritide vs. placebo will each be conducted using a Type I error rate of 0.025.

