5. BASIC STUDY DESIGN

This study is a randomized, double blind, placebo controlled, multi-center clinical trial of patients with signs and symptoms consistent with AHF within 24 hours of hospital admission. A total of approximately 360 patients will be enrolled in the trial.

Patients will be randomized to one of 3 treatment regimens (120 patients / treatment regime):

- 1. Optimal diuretic dosing + placebo
- 2. Optimal diuretic dosing + low dose dopamine
- 3. Optimal diuretic dosing + low dose nesiritide

Central venous line or PICC line or standard peripheral IV catheter placed in the antecubital fossa, depending on local hospital requirements, will be placed in the patients randomized to the Dopamine strategy group. Standard peripheral IV catheter will be placed in the patients randomized to the Nesiritide strategy group

ROSE protocol Amendment 1: March 24, 2011

TThere will be an initial open 1:1 randomization to a Nesiritide Strategy group or a Dopamine Strategy group. Patients in the Dopamine Strategy group will subsequently be randomized to low dose dopamine or placebo in a 2 to 1 blinded fashion. Likewise patients in the Nesiritide Strategy group will be randomized to low dose nesiritide or placebo in a 2 to 1 blinded fashion. All patients will receive open-label diuretic treatment.

Figure 4

For testing the primary hypotheses outlined in Section 2.1, the placebo patients will be pooled, so that patients randomized to receive dopamine will be compared with the pooled placebo group, and similarly, patients randomized to receive nesiritide will be compared to the pooled placebo group.

The study treatment regimen will be administered for *a total duration of* 72 hours, unless clinical reasons require discontinuation earlier.

The investigator may modify the diuretic dose at 24 and / or 48 hours. The primary assessment for both efficacy and safety will occur at 72 hours after randomization. **After** the primary assessment at 72 hours, all treatment will be open label at the treating physician's discretion.

The primary safety endpoint will be change in serum cystatin C from randomization to 72 hours, based on a standardized, blinded core lab assessment. The primary endpoint for efficacy will be cumulative urinary volume (UV; indwelling urinary catheter) at 72 hours.

Patients will be followed daily during hospitalization for assessment of serious adverse events.

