9.1 Randomization

After providing informed consent and signing the ICF, all study subjects will be randomized using procedures determined by the DCC to one of 3 treatment groups. **Patients will be randomized to the nesiritide or dopamine strategy in a 1:1 allocation ratio.** Within each strategy, subjects will be randomized to active drug vs. placebo in a 2:1 allocation ratio. A permuted block randomization method stratified by site will be used to ensure relatively equal distribution of subjects to each arm within each clinical site.

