13.3 Sample Size Justification

A difference of 0.3 mg/L in serum cystatin C is considered to be clinically meaningful. With a conservative estimate of 102 subjects per treatment group and a standard deviation for the change between randomization and 72 hours of 0.62 mg/L (see Owan et.al. 2008 for an estimate at 48 hours)¹⁸, the study would have 88% power to detect a clinically significant difference between low-dose dopamine vs. placebo (or low-dose nesiritide vs. placebo) at the 0.025 two-sided level. A standard deviation for the change of 0.59 mg/L would provide 91% power and any standard deviation of less than 0.68 mg/L would provide greater than 80% power to detect a clinically meaningful difference. Based on prior Heart Failure Network clinical trials, the amount of missing data is expected to be less than 15% for the change in serum cystatin C from randomization to 72 hours. Therefore a sample size of 120 subjects per treatment group will provide adequate power for the serum cystatin C analyses.

In the clinical trial of Owan et.al.¹⁸ the estimated standard deviation for the change in cumulative fluid balance from randomization to 72 hours was approximately 2900 mL.¹⁸ Based on prior Heart Failure Network clinical trials, the amount of missing data is expected to be less than 10% for the cumulative UV at 72 hours. With a Type I error rate of 0.025 and a sample size of 108 evaluable subjects per treatment arm, the study would have 90% power to detect a treatment difference of > 1400 mL and 80% power to detect a difference of > 1224 mL. These power calculations were based on a 2-sample t-test for the hypothesis of equal means.

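### The strategy indicator in the primary model conflicts with the pooled placebo comparison: unless a pooled contrast is named, power is about 71% and 74%, not 88% and 90%

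*Protocol*

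**What the plan says.** Section 9.1 describes two stages of randomisation. First, "Patients will be randomized to the nesiritide or dopamine strategy in a 1:1 allocation ratio"; then active drug or placebo, 2:1, within the strategy. Section 5 gives 120 patients per treatment, so each strategy holds 120 active and 60 placebo patients. Dopamine occurs only in the dopamine strategy and nesiritide only in the nesiritide strategy.

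Section 13.2 specifies the primary analysis as "A general linear model with an indicator for randomization to the nesiritide strategy or dopamine strategy, as well as an indicator for the specific treatments". It continues: "For the primary comparisons, placebo subjects will be pooled across the nesiritide and dopamine strategies". The two drug-versus-placebo comparisons "will each be conducted using a Type I error rate of 0.025". Section 5 says the same about the control group: "For testing the primary hypotheses outlined in Section 2.1, the placebo patients will be pooled".

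Section 13.3 computes power "at the 0.025 two-sided level" with 102 evaluable patients per group for cystatin C and 108 per group for urine volume, and adds: "These power calculations were based on a 2-sample t-test for the hypothesis of equal means". That is one drug against all placebo patients, with no strategy term.

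**The concern.** A strategy indicator separates the two placebo subgroups; pooling puts them together. Because each drug is nested in one strategy, a model holding both kinds of indicator estimates the drug effect inside that strategy only. An analyst who fits the model of Section 13.2 and reads off the treatment coefficient gets a comparison with half the control group that Sections 5 and 13.3 assume.

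Both co-primary endpoints and both drugs are affected. The two estimators differ in precision. If the open strategy assignment or the type of vascular access affects outcome, they also differ in what they estimate. Leaving the choice open in the protocol means it could be made after the results of both are known.

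**Working it through.** **Inputs.** Two-sided level 0.025 (Sections 13.2 and 13.3). Allocation 1:1, then 2:1 (Section 9.1). Cystatin C: difference 0.3 mg/L, SD 0.62 mg/L (alternatives 0.59 and 0.68), 102 evaluable per group. Urine volume: differences 1400 and 1224 mL, SD 2900 mL, 108 evaluable per group (all Section 13.3). Assumption, not in the protocol: missing data fall in proportion to allocation, so each strategy has 51 evaluable placebo patients for cystatin C and 54 for urine volume.

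**Step 1. Reproduce the stated power.** With equal groups, SE = SD × √(2/n), and power comes from the noncentral t with noncentrality difference/SE.
- Cystatin C: √(2/102) = 0.1400; 0.3/(0.62 × 0.1400) = 3.46; power 88.3%.
- Urine volume, 1400 mL: √(2/108) = 0.1361; 1400/(2900 × 0.1361) = 3.55; power 90.1%.

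All five stated figures reproduce (table below), so Section 13.3 is right for the test it describes.

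**Step 2. What the model's treatment coefficient estimates.** Let S = 1 in the dopamine strategy, D = 1 on dopamine, N = 1 on nesiritide, with mean a + s·S + d·D + n·N. The four cell means are:
- dopamine: a + s + d
- placebo in the dopamine strategy: a + s
- nesiritide: a + n
- placebo in the nesiritide strategy: a

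Four parameters fit four cells exactly, so d is the dopamine mean minus the dopamine-strategy placebo mean. The least-squares weights are +1/102 per dopamine patient, −1/51 per dopamine-strategy placebo patient and 0 for everyone else. Nesiritide mirrors this. Fitting only one drug plus both placebo subgroups gives the same weights (three parameters, three cells).

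**Step 3. Standard error.** √(1/102 + 1/51) = 0.1715 SD, against 0.1400 SD when pooled. The variance ratio is 1.5 and the SE ratio √1.5 = 1.22. For urine volume, √(1/108 + 1/54) = 0.1667 SD against 0.1361 SD.

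**Step 4. Power if that coefficient is the test.** The noncentrality is 0.3/(0.62 × 0.1715) = 2.82 for cystatin C and 1400/(2900 × 0.1667) = 2.90 for 1400 mL. Ranges run from two-group degrees of freedom to those of the four-cell model.

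| Endpoint | Stated | Pooled, reproduced | Coefficient, evaluable numbers | Coefficient, no missing data (120 vs 60) |
|---|---|---|---|---|
| Cystatin C 0.3, SD 0.62 | 88% | 88.3% | 71.1–71.5% | 78.7–79.0% |
| Cystatin C 0.3, SD 0.59 | 91% | 91.4% | 75.8–76.2% | not computed |
| Cystatin C 0.3, SD 0.68 | over 80% for any smaller SD | 81.3% | 62.2–62.6% | not computed |
| Urine volume 1400 mL | 90% | 90.1% | 73.6–74.0% | 78.5–78.8% |
| Urine volume 1224 mL | 80% | 80.0% | 60.7–61.1% | 65.9–66.2% |

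**Step 5. Can the same model give the pooled comparison?** Yes, through the contrast active mean minus the average of the two placebo means. For dopamine its variance is 1/102 + ¼(1/51 + 1/51) = 2/102, so the SE is 0.1400 SD and the stated power returns. In the model's terms the contrast is (a + s + d) − (a + s/2) = d + s/2; for nesiritide it is (a + n) − (a + s/2) = n − s/2. Half of any strategy effect therefore enters each drug comparison, with opposite signs, and the strategy term no longer adjusts either one.

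**The case against.** A linear model does not oblige anyone to test its raw coefficient. Section 13.2 names a model and then says how the primary comparison is formed, by pooling placebo. Section 5 repeats the pooling and Section 13.3 powers for it. Read as the contrast in Step 5, all three agree and the stated power is correct. The coding of a contrast is also the kind of detail that often goes into an analysis plan, and that plan is not at hand.

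Much of this stands. A reader might infer that the model and the pooling cannot both be primary, or that the trial will be analysed with power near 71%. The documents support neither: the contrast reconciles the two sentences, and nothing shows which quantity will be tested. The low power figures are conditional on the coefficient being the test.

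Two things remain. Section 13.2 does not name the contrast, and the ordinary reading of a model with a strategy indicator and treatment indicators used to examine each treatment's effect is the within-strategy coefficient. And under the contrast the strategy term does no adjusting, so a reader who sees it in the model would be misled about what was controlled. This goes beyond detail left for later: the protocol states a model whose plain output disagrees with its own pooling rule and its own sample-size basis.

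Section 13.5 already plans a comparison of the two placebo subgroups to look for an effect of the PICC line. That helps to judge whether pooling is reasonable, but does not say which estimate is primary.

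**Conclusion.** The point holds as a conflict in the wording of the primary analysis. As written, the treatment coefficient of the Section 13.2 model uses 60 of the 120 randomised placebo patients, while Sections 5 and 13.3 rely on all 120. If that coefficient is the primary test, the chance of missing a true 0.3 mg/L difference at SD 0.62 rises from about 12% to about 29%, with similar losses for urine volume. The stated power holds only for the pooled comparison.

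The 71% and 74%/61% figures use the protocol's effects, SDs and evaluable numbers, and assume losses proportional to allocation. Section 13.3 expects losses below 15% and 10%, so they sit at the low end; the no-missing-data figures (about 79% for cystatin C, 79%/66% for urine volume) are the upper end under the same SDs. The 1.5 variance ratio follows from the allocation and depends on neither effect size nor SD.

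**What to change.** Make Section 13.2 match Sections 5 and 13.3 in one of two ways:
- remove the strategy indicator from the primary model, so that each drug is compared with all placebo patients; or
- keep the model and state that the primary contrast is the active mean minus the average of the two placebo means.

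With either, report the within-strategy (strategy-adjusted) estimate as a named sensitivity analysis. The cost is a sentence or two and one extra analysis, with no change to conduct, data collection or sample size. The downside is that the pooled comparison carries half of any effect of open strategy assignment or line placement. The sensitivity analysis and the placebo-versus-placebo comparison in Section 13.5 would show it, though the latter is imprecise: with 51 per subgroup its SE is √(2/51) = 0.198 SD, or 0.12 mg/L at SD 0.62.

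Alternatively, keep the strategy-adjusted coefficient as primary, delete the pooling statements in Sections 5 and 13.2, and restate power at about 71% for cystatin C and 74%/61% for urine volume. This protects against a strategy effect but costs power. By the normal approximation, restoring 88% for cystatin C would need about 75 placebo and 150 active evaluable patients per strategy (450 in all, against 3 × 102 = 306). Restoring 90% at 1400 mL would need about 80 and 160 (480 in all, against 3 × 108 = 324).
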